13.0 Regulatory Considerations

13.1 Protocol Review and Amendments

This protocol, the proposed informed consent and all forms of participant information related to the study (e.g., advertisements used to recruit participants) and any other necessary documents must be submitted, reviewed and approved by a properly constituted IRB governing each study location.

Any changes made to the protocol must be submitted as amendments and must be approved by the IRB prior to implementation. Any changes in study conduct must be reported to the IRB. The DF/HCC Overall Principal Investigator (or Protocol Chair) will disseminate protocol amendment information to all participating investigators.

All decisions of the IRB concerning the conduct of the study must be made in writing.

13.2 Informed Consent

All participants must be provided a consent form describing this study and providing sufficient information for participants to make an informed decision about their participation in this study. The formal consent of a participant, using the IRB approved consent form, must be obtained before the participant is involved in any study-related procedure. The consent form must be signed and dated by the participant or the participant's legally authorized representative, and by the person obtaining the consent. The participant must be given a copy of the signed and dated consent document. The original signed copy of the consent document must be retained in the medical record or research file.

13.3 Ethics and Good Clinical Practice (GCP)

This study is to be conducted according to the following considerations, which represent good and sound research practice:

 E6 Good Clinical Practice: Consolidated Guidance www.fda.gov/downloads/RegulatoryInformation/Guidances/UCM12951 5.pdf

- US Code of Federal Regulations (CFR) governing clinical study conduct and ethical principles that have their origin in the Declaration of Helsinki
 - Title 21 Part 11 Electronic Records; Electronic Signatures www.access.gpo.gov/nara/cfr/waisidx 02/21cfr11 02.html
 - Title 21 Part 50 Protection of Human Subjects www.access.gpo.gov/nara/cfr/waisidx_02/21cfr50_02.html
 - Title 21 Part 54 Financial Disclosure by Clinical Investigators www.access.gpo.gov/nara/cfr/waisidx_02/21cfr54_02.html
 - Title 21 Part 56 Institutional Review Boards www.access.gpo.gov/nara/cfr/waisidx_02/21cfr56_02.html
 - Title 21 Part 312 Investigational New Drug Application www.access.gpo.gov/nara/cfr/waisidx_02/21cfr312_02.html
- State laws
- DF/HCC research policies and procedures http://www.dfhcc.harvard.edu/clinical-research-support/clinical-research-unit-cru/policies-and-procedures/

It is understood that deviations from the protocol should be avoided, except when necessary to eliminate an immediate hazard to a research participant. In such case, the deviation must be reported to the IRB according to the local reporting policy.

13.4 Study Documentation

The investigator must prepare and maintain adequate and accurate case histories designed to record all observations and other data pertinent to the study for each research participant. This information enables the study to be fully documented and the study data to be subsequently verified.

Original source documents supporting entries in the case report forms include but are not limited to hospital records, clinical charts, laboratory and pharmacy records, recorded data from automated instruments, microfiches, photographic negatives, microfilm or magnetic media, and/or x-rays.

13.5 Records Retention

All study-related documents must be retained for the maximum period required by applicable federal regulations and guidelines or institutional policies.

13.6 Multi-center Guidelines

N/A

14.0 STATISTICAL CONSIDERATIONS

14.1 Target Sample Size

Forty patients will be entered in this phase II study. Assuming the accrual rate is 2-3 patients per month, the accrual will be completed in 18 months or less.

- 14.2Planned Efficacy Evaluations
 - 14.2.1 Primary Efficacy Variables

The primary objective of this study is time to tumor progression (TTP). A sample size of 40 achieves 80% power to detect the difference between the null hypothesis median TTP of 5 months and an alternative hypothesis median TTP of 7 months at a 10% significance level using a one-sided test based on the elapsed time, assuming a study follow-up period of 24 months. The total study duration will be 42 months (18 months of accrual + 24 months of follow-up).

14.2.2 Secondary Efficacy Variables

The secondary objectives are to assess the toxicity profiles of this regimen and the preliminary data on response rate and overall survival. Overall survival is defined as the time from study entry until death from any cause. Overall survival will be calculated using the Kaplan-Meier method, and confidence limits for survival estimates will be calculated using the Greenwood formula. Progression free survival is defined as the time from study entry until disease progression or death from any cause. Response rate is defined as the percentage of patients achieving either CR or PR. Duration of response is defined as the time interval from the initial response to the time disease progression is observed.

All categories of toxicity and complications of the treatment will be recorded. Toxicity and complications of the treatment will be assessed based on reports of adverse events, physical examinations, and laboratory measurements.

REFERENCES/BIBLIOGRAPHY

3. Llovet JM, Bruix J: Molecular targeted therapies in hepatocellular carcinoma. Hepatology 48:1312-27, 2008

APPENDIX A: CLIP score and CTP classification

CLIP Score				
Variables	0	1	2	
CTP score	A	В	С	
Tumor Morphology	Solitary & extension = 50%</td Multiple & extension < /= 50%	Massive or extension > 50%	Multiple & extension < /= 50%	Massive or extension > 50%	
AFP	<400	> 400		
PV thrombosis	No	Yes		

Child-Turcotte-Pugh (CTP) Classification

		Points	
	1	2	3
Bilirubin	< 2	2-3	>3
Albumin	>3.5	2.8-3.5	<2.8
Prothrombin ti	me <4	4-6	>6
Encephalopat	hy None	1-11	III-IV
Ascites	None	Slight	Moderate
Grade A	CTP score 5-6		
Grade B	CTP score 7-9		
Grade C	CTP score 10-15		

APPENDIX B: Barcelona Clinic Liver Cancer (BCLC) Staging

BCLC Staging and Treatment Strategy

Llovet, J. M. et al. J. Natl. Cancer Inst. 2008 100:698-711

Appendix C: Correlative Studies on Plasma Biomarkers

Exploratory analyses of potential biomarkers of sorafenib activity will be performed by measuring proteins in the plasma on Day 1 (prior to first dose of sorafenib later that day) and Day 3 of lead-in phase, and on C1D1, C1D15 and C1D29 of FOLFOX-Sorafenib, and if available, at the time of progression. Plasma analysis will be carried out for a panel of circulating angiogenic and inflammatory molecules previously identified by others and us as potential biomarkers of response in HCC. They include soluble VEGFR1 (sFLT1), VEGF, placental-derived growth factor (PIGF), basic fibroblast growth factor (bFGF), interleukin (IL)-1 β , IL-6, IL-8, and tumor necrosis factor $\Box \alpha$ (TNF- α) using 2 multiplex protein array plates from Meso-Scale Discovery (Gaithersburg, MD), soluble VEGFR2, angiopoietin 2 (ANG2), HGF hepatocyte growth factor (HGF), soluble c-KIT, carbonic anhydrase 9 (CAIX) and stromal-derived factor 1 α (SDF1 α) from R&D Systems (Minneapolis, MN). Samples will be run in duplicate.

Supplies

The following supplies are needed for each blood sample drawn:

• EDTA blood collection tubes (Sarstedt, #03.1068)

Sample Labels

Prior to use, EDTA tubes should be labeled with the following information:

- Patient Initials
- Patient ID number
- Protocol number
- Collection date
- Institution

Collection and handling (Please see attached Biomarker Manual for full details) Approximately 8 cc of venous blood will be collected in each of 2 EDTA blood collection tubes (Sarstedt, #03.1068). The tubes should be gently inverted several times to ensure mixing with the anticoagulant and kept on wet ice at all times. Within two hours the tubes should be sent to:

Steele Laboratory

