1.0 Objectives

- 1.1 Primary Objective
- To assess the time to progression (TTP) in patients with HCC treated FOLFOX-S.
- 1.2 Secondary Ojective
 - To evaluate the tolerability and toxicities of FOLFOX-S regimen in this population of patients.
 - To assess the response rate, the duration of response, median PFS, and median OS of FOLFOX-S in patients with HCC.

• To assess changes of angiogenic and inflammatory parameters with treatment of sorafenib.

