2.5 Study Rationale

HCC are commonly viewed as highly vascular tumors ¹⁵. Vascular endothelial growth factor (VEGF) is a potent angiogenesis stimulator and an important regulator in pathological angiogenesis. Increased levels of VEGF have been found in tumor and serum of patients with HCC. Increased VEGF expression has been associated with inferior survival in HCC. Thus, inhibition of VEGF and its receptor is a logical target in the treatment of patients with HCC. Sorafenib (S) has emerged as the new standard treatment for patients with advanced HCC based on the improvement of overall survival benefits. However, the benefits of sorafenib are still modest. Combining doxorubicin with sorafenib has shown encouraging results in comparison with doxorubicin with placebo in a randomized phase II study ¹⁶. Median TTP was 6.4 months in the sorafenib-doxorubicin group (95% confidence interval [CI], 4.8-9.2), and 2.8 months (95% CI, 1.6-5) in the doxorubicin-placebo monotherapy group (P = .02). Median OS

was 13.7 months (95% CI, 8.9-not reached) and 6.5 months (95% CI, 4.5-9.9; P = .006). FOLFOX has shown more favorable efficacy results when compared with doxorubicin (Improved RR and PFS and a trend of OS improvement) in a randomized phase III study conducted in Asia as discussed in Section 2.2.

In this study, we will examine the efficacy and tolerability of combining FOLFOX with sorafenib. As a multitargeted tyrosine kinase inhibitor with antiangiogenic activity, sorafenib may enhance chemotherapy-induced tumor kill by the destruction of tumor blood vessel as well as by inducing "normalization" of tumor vasculature with improved delivery of therapeutics. During the first 2 weeks of treatment with sorafenib alone, we will also examine changes induced by sorafenib 1) in plasma angiogenic and inflammatory markers with serum biomarkers and 2) specific changes in the tumor and surrounding non-cancer liver tissues with optional on-treatment biopsies.

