5.0 STUDY DESIGN

- 5.1Treatment Plan
- 5.1.1 Single arm, open label, phase II study
- 5.1.2Dosing schedule

Treatment will be administered on an outpatient basis. Expected adverse events and appropriate dose modifications for sorafenib, 5-FU, oxaliplatin are as described in Section 6.0. No investigational or commercial agents of therapies other than those described below may be administered with the intent to treat the patient's malignancy.

Patients will be treated as below:

Register:

Sorafenib 400 mg bid \rightarrow	Sorafenib 400 mg bid	\rightarrow	continue treatment
First two weeks	modified folfox, days 1, 15	5	until PD or intolerable toxiity

Every 28 days/cycle

For first two weeks, sorafenib will be given alone.

Cycle 1 and beyond:

Sorafenib 400 mg bid + modified FOLFOX (Oxaliplatin 85 mg/m2 followed by leucovorin 200 mg/m², followed by infusional 5-FU at 1200 mg/m²/d on Days 1 and 2 (2400 mg/m² total over 46 hours) repeated every 14 days for each cycle.

Oxaliplatin will be delivered at 85 mg/m²as a 2-hour infusion on day 1 and day 15 of every cycle.

Drugs 5-FU/LV		Oxaliplatin	Sorafenib
Treatment dates	Days 1,15	Days 1,15	Daily (days 1-28)
Dosage	LV: 200 mg/m2 5-FUCI: 2400 mg/m ² total (1200mg/m ² /d on day 1 and 2)	85 mg/m2	400 mg bid

Lead-in sorafenib alone treatment: first 2 weeks.

Each cycle is defined as 28-day treatments.

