5.2.3 Post-Treatment Evaluations

- All patients will be evaluated by history and physical examination, including vital signs, weight, and performance status, CBC with differential, chemistries, and reassessment of tumor at the end of treatment.
- Female patients of childbearing potential will be evaluated with a repeat pregnancy test at end of treatment visit.
- All sites of tumor progression and metastasis will be recorded.
- Progression-free and overall survival will be determined.
- 5.2.4 Correlative Studies
 - Only patients getting their treatment at MGH will be eligible for the correlative studies given that all samples need to be processed at the Steele Lab at MGH.
 - BASELINE AND ON-TREATMENT PLASMA STUDIES (see Appendix C for details): Circulating endothelial cells and plasma levels of growth factors will be assessed:
 - On Day 1 (prior to the first dose of sorafenib) and Day 3 of lead-in phase
 - On C1D1, C1D15, and C1D29 of FOLFOX-Sorafenib. The Day 3 correlative can be drawn on Day 3, 4, or 5. The Day 15 correlative can be drawn on Day 14, 15, or 16. The Day 29 correlative can be drawn on Day 27, 28, or 29.
 - At the time of progression if available

 ON-TREATMENT OPTIONAL BIOPSY (see Appendix D for details): All patients enrolled on this trial are required to have a baseline diagnostic biopsy for histological confirmation of HCC. To be considered for the optional posttreatment tumor biopsy, the patient must have adequate tissue on their baseline biopsy (i.e. core biopsy) to have all necessary correlative studies run on the sample. The optional posttreatment tumor biopsy will be obtained any time from Day 10 to Day 14 of the lead-in phase in patients who consent to a posttreatment tumor biopsy (n=6-12).

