Appendix D: Tissue Collection Protocol

To be considered for the optional posttreatment tumor biopsy, the patient must have adequate tissue on their baseline biopsy (i.e. core biopsy) to have all necessary correlative studies run on the sample. The treating physician must also deem them to be a reasonable candidate for tumor biopsy based on laboratory and clinical evaluation. The optional posttreatment tumor biopsy will be obtained any time from Day 10 to Day 14 of the lead-in phase in patients who consent to a posttreatment tumor biopsy (n=6-12). Only patients getting their treatment at MGH will be eligible for the posttreatment biopsy and the biopsy-related correlative studies given that all samples need to be processed at the Steele Lab.

Gene expression profiles on the biopsy on the baseline and posttreatment biopsy samples will be assessed by laser capture microdissection (LCM) and quantification of genes by qPCR. These analyses will provide the first glimpse into the mechanism of action of sorafenib in HCC.

Supplies:

Tissue-Tek ®: Cryomold

- Standard size 25x20x5mm (#4557)

 Fisher Scientific Cat# NC9511236
 OR
- Intermediate size 15x15x5mm (#4566)
 - Fisher Scientific Cat# NC9542860

Tissue-Tek ®: O.C.T. Compound, 4oz (#4583): Fisher Scientific Cat# NC9638938

Small specimen bag: Fisher Cat# 01-002-37 (or equivalent) Forceps: Fisher Cat# NC9832137 (or equivalent) Dry Ice and Cooler Cryoware Pen: Fisher Cat# 13-382-88

Procedure:

1. Bring all supplies needed to the biopsy as the tissue needs to be frozen **immediately**.

2. Squeeze small amount of OCT into cyromolds* – enough for there to be a thin layer covering the bottom.

3. As soon as the specimen is ready, use disposable forceps to gently place only 1 core into each cryomold.

4. You should ideally collect between 3 and 5 separate cores.

5. Once the specimen is in the cryomold, cover with more OCT making sure the tissue is entirely submerged.

6. Immediately place cryomold with OCT and tissue onto dry-ice making sure the cryomold is level and will not tip over.

7. The OCT will freeze into a solid white block within 5-10 minutes

8. Once the blocks have completely frozen they can be put into a specimen bag and sealed. More than one block can be put into a bag.9. The bag should be labeled with:

a. Patient name
b. MGH Study #: 12-218
c. MGH MRN #
d. Date of biopsy
e. Time Point (Biopsy #1, Biopsy #2, etc)
f. Number of blocks in the bag

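### In biopsied patients the only two-week sorafenib-alone plasma sample nominally follows the optional biopsy by 1 to 5 days; draw it first, and name the sorafenib-alone contrasts in Appendix C

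*Combined protocol and SAP*

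**What the plan says.** The secondary objective in Section 1.2 is "To assess changes of angiogenic and inflammatory parameters with treatment of sorafenib". Section 2.5 ties this to the lead-in: "During the first 2 weeks of treatment with sorafenib alone, we will also examine changes induced by sorafenib". Section 5.1.2 sets the lead-in: "For first two weeks, sorafenib will be given alone". FOLFOX starts on C1D1 and is repeated on Day 15 of each 28-day cycle, in a single-arm trial.

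Appendix C introduces the plasma work with "Exploratory analyses of potential biomarkers of sorafenib activity will be performed by measuring proteins in the plasma on Day 1". It continues through lead-in Day 3 "and on C1D1, C1D15 and C1D29 of FOLFOX-Sorafenib, and if available, at the time of progression". The panel includes IL-1β, IL-6, IL-8, TNF-α, VEGF and HGF. Section 5.2.2 requires assessments other than imaging to be done before study drug is given, and allows a general window of 3 days either side.

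On the biopsy, Section 5.2.4 and Appendix D state: "The optional posttreatment tumor biopsy will be obtained any time from Day 10 to Day 14 of the lead-in phase". The planned number is 6 to 12 consenting patients, and Appendix D adds: "You should ideally collect between 3 and 5 separate cores". Both the plasma work and the biopsy are limited to patients treated at one hospital, whose number is not given. Section 14 describes no biomarker analysis, and Section 8 only points to Appendix C.

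**The concern.** The lead-in gives the trial a period in which marker change can be ascribed to sorafenib without FOLFOX. Within it there are two plasma samples after baseline, one at about Day 3 and one at two weeks. The two-week sample is the only one that shows the effect of sustained sorafenib. In patients who have the on-treatment biopsy, the nominal schedule puts needle cores into the tumor a few days before that sample. The panel consists of inflammatory and angiogenic proteins, which tissue injury could plausibly move. A rise at C1D1 in such a patient could then come from sorafenib or from the biopsy. None of the provided text puts the draw first or says how biopsied patients are handled in the plasma analysis.

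A second, smaller matter is the label. Appendix C places every draw under sorafenib activity, including those taken after FOLFOX has started. In a single arm those later changes cannot be divided between the two treatments.

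**Working it through.** The plan gives no sample size, power or effect size for the plasma objective, so there is no stated figure to reproduce. The check is day arithmetic.

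**Inputs.** Lead-in of two weeks, Days 1 to 14, so C1D1 is nominal Day 15 (Section 5.1.2). Biopsy on Day 10 to 14, in 6 to 12 patients (Section 5.2.4, Appendix D). Day 3 draw allowed on Day 3, 4 or 5 (Section 5.2.4). General window ±3 days (Section 5.2.2). Trial size 40 (Section 14.1).

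**Where each draw falls.** Gap = draw day − biopsy day.

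| Draw | Nominal day | FOLFOX doses before it | Position relative to biopsy |
|---|---|---|---|
| Day 1 | 1 | 0 | before |
| Day 3 | 3 to 5 | 0 | 10−5 = 5 to 14−3 = 11 days before |
| C1D1, pre-dose | 15 | 0 | 15−14 = 1 to 15−10 = 5 days after |
| C1D15 | 29 | 1 | 29−14 = 15 to 29−10 = 19 days after |
| C1D29 | 43 | 2 | 43−14 = 29 to 43−10 = 33 days after |
| Progression | varies | usually at least 1 | varies |

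C1D1 has no draw window of its own. If the general ±3 days applies, the draw falls on Day 12 to 18 and the gap runs from 12−14 = −2 to 18−10 = +8 days. The order of draw and biopsy is then not fixed at all.

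**Contrasts free of both FOLFOX and the on-treatment biopsy.** Day 1 to Day 3 in every sampled patient, and Day 1 to pre-dose C1D1 in unbiopsied patients. Only Day 1 to C1D1 in biopsied patients is open to question.

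**Share affected.** If all 40 give plasma: 6/40 = 15% to 12/40 = 30%, leaving 40−12 = 28 to 40−6 = 34 unbiopsied. If 20 do (an assumption, because the hospital's number is not stated): 6/20 = 30% to 12/20 = 60%, leaving 8 to 14.

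**Illustration of size.** Shift in the all-patient mean change = share biopsied × biopsy effect. An effect of 0.5 SD at C1D1 is purely an assumption. It gives 0.15 × 0.5 = 0.075 to 0.30 × 0.5 = 0.15 SD with 40 patients, and 0.30 × 0.5 = 0.15 to 0.60 × 0.5 = 0.30 SD with 20. If biopsy has no effect on these markers, the shift is zero.

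**The case against.** The strongest reply is that the objective is largely intact. A reader might infer from the schedule that the whole sorafenib-change objective is confounded. The documents do not support that, because two of the contrasts above are clean. A reader might also infer that Appendix C attributes post-FOLFOX changes to sorafenib. It does not say so: it lists draw times, defines no contrast, and itself describes the later draws as belonging to the combination. Section 2.5 already restricts sorafenib-induced change to the lead-in. Both replies stand, and the label therefore needs alignment rather than a new analysis.

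Next, nothing in the documents says that needle cores move any panel marker, in which direction, or for how long. That also stands: the mechanism is plausible but assumed. The 3 to 5 cores are an ideal, the biopsy is optional, and 1 to 5 days is the nominal gap only.

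It can also be said that the problem is recoverable. Appendix C has the tubes labelled with collection date and Appendix D has the tissue labelled with biopsy date, so biopsied patients and their actual gaps can be identified and set aside. This stands in part. Setting them aside costs 6 to 12 patients. The remainder is also a selected group, since biopsy depends on consent, baseline tissue and the physician's judgement, so a difference with and without them would not be a pure biopsy effect. One might add that plasma and tissue changes were to be linked in these same patients, but no section plans such a linkage, so the point does not rest on it.

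Finally, drawing before biopsy makes the two-week sample 1 to 5 days earlier in biopsied patients than in others. That is a real but small cost. Appendix C also refers to a Biomarker Manual that is not among the documents and might already fix the order.

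**Conclusion.** The point holds in a limited form. In the 6 to 12 biopsied patients, the Day 1 to C1D1 change may mix sorafenib with biopsy injury, because the draw nominally follows the biopsy by 1 to 5 days and neither Section 5.2.4 nor the appendices order them. The share is 15% to 30% if all 40 patients give plasma, and larger if the single hospital contributes fewer. The conclusion rests on three assumptions: the nominal schedule is followed, the pre-dose rule in Section 5.2.2 covers the C1D1 draw, and biopsy can move at least some of the panel markers within days. The last has no figure in the documents.

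The analyses are exploratory, and the primary TTP analysis and sample size are untouched. This is an inexpensive improvement to the plan, not a flaw that undermines the trial.

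**What to change.** In Section 5.2.4 and Appendix C:

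1. For patients having the optional biopsy, draw the two-week lead-in plasma immediately before the biopsy, on the biopsy day (Day 10 to 14, still sorafenib alone). For all others keep C1D1, and state there that it is drawn before dosing.
2. Report the two-week change with and without biopsied patients. This also checks whether the slightly earlier draw matters.
3. Name the sorafenib-alone contrasts as Day 1 to Day 3 and Day 1 to the two-week sample before FOLFOX, in line with Section 2.5. Describe C1D15, C1D29 and, in most cases, the progression draw as change under the combination.

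If samples have already been collected, items 2 and 3 still apply, using the recorded dates to identify biopsied patients and their actual gaps.

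The cost is a few sentences and a re-timed, not added, blood draw in 6 to 12 patients at one hospital. Any Biomarker Manual should be brought into agreement.
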